# **10.2** Secondary Analyses

Summary scores will calculated for each questionnaire as outlined in Section 9.2. Summary statistics for the SIS-SF, EQ-5D-5L, ICECAP-A, SSSQ and HLQ scores will be produced in Tables 5.15-5.34. Analysis from these questionnaires and scores will be included in the HEAP.

It should be noted that these secondary analyses are exploratory and that the sample size is enough to power the primary analyses only.

#### 10.2.1 Intervention Sub-group and Fidelity Analysis

The intervention cohort will be considered as a separate sub-group analysis with an *a priori* hypothesis that the 'dose' level of intervention is associated with outcome SIS emotion/ handicap score. Exposure to the intervention is difficult to summarise succinctly as some aspects of the intervention are optional, and patients in the intervention arm can therefore decide, to some extent, which aspects of the package of care available to them they wish to receive.

Consideration will be given to participants in the intervention as a separate sub-group analysis in three areas: 1) Structured stroke review, 2) MLAS and 3) Fidelity.

#### 1) Structured Stroke Review

There is an *a priori* hypothesis that stroke review attendance and the level of action taken at a stroke review is associated with SIS handicap and emotion 12 month score. A linear mixed effect model will be fitted in line with the primary analysis with fixed effects for the stroke review attendance (y/n), and categorical variable for action taken (no review, review with no action plan, review with action plan).

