# **10.1 Primary Efficacy Analyses**

The standardised domain total scores will be calculated (as described in section 9.2.1) for each of the two co-primary outcomes (SIS emotional domain and SIS handicap domain). The analyses will focus on the evidence for a difference in SIS score (handicap or emotion) between the intervention and control group.

Each domain will be modelled separately and the following model fitted:

$$Y_i = \beta_0 X_{0i} + \beta_1 X_{1i} + \epsilon_i$$

For each co-primary outcome there is the potential for clustering and therefore a mixed effect model will be fitted with a random effect for general practice and fixed effects for the treatment group to assess the effect of clustering:

$$Y_{ij} = \beta_0 X_{0ij} + \beta_1 X_{1ij} + u_j + \epsilon_{ij}$$

Where,

Yij = continuous outcome SIS score (emotion/ handicap domain)

*i* = individual patient

j = cluster/ practice

 $X_1$  = dummy variable for the intervention treatment group.

X0 = baseline covariates (baseline score, gender, cluster size, time since last stroke at consent)

 $\beta_0$  = intercept which represents the population average SIS score

 $\beta_1$  = difference in score between intervention and control groups at 12 months

 $u_i \sim N_1(0, \sigma_h^2)$  is the cluster-level random practice effect

 $\epsilon_{ii} \sim N_1(0, \sigma_e^2)$  is the residual error

There is an a priori hypothesis that the following covariates may be associated with the co-primary outcomes: gender, age at baseline (categorical), time since last stroke (categorical), general practice list size (the stratifying variable used in the randomisation, split into two categories; <10,500 and  $\geq$ 10,500 patients) and deprivation score (continuous, both at the patient and practice level). Once the primary analysis model is decided, these covariates will be added to assess and changes in treatment effect on the co-primary outcomes.

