#### 2) MLAS

Participants in the intervention group can only attend MLAS if they have attended a structured stroke review. A linear mixed effect model will be fitted in line with the primary analysis with fixed effects for gender, baseline score and categorical variable MLAS compliance (yes, partial, no), where

- Complete an individual attended both individual appointments and at least 3 of the 4 group sessions (including group session 1).
- Incomplete an individual has attended at least 1 session (either an individual appointment or group session).
- No an individual has not attended any MLAS sessions.
- 3) Intervention fidelity

The trial team will collect data on intervention fidelity (Table 4) to monitor exposure and quality of various aspects of the intervention as follows:

 Fidelity of training – Audio-recorded training sessions (IPCAS) will be scored against a prespecified checklist containing planned curriculum content and materials (n= 16 items). Three response options are used: done (2 points), partially done (1 point) and not done (0 points). Video-recorded training sessions (MLAS) will be scored against a pre-specified checklist containing planned curriculum content and materials (n= 205 items). Three response options are used: present (2 points), attempted (1 point) and absent (0 points).

- Fidelity of delivery Audio-recorded structured reviews will be scored against a pre-specified checklist (n= 9 items). Three response options are used: done (2 points), partially done (1 point) and not done (0 points). Self-reported structured reviews will be scored against a pre-specified checklist (n= 9 items). Three response options are used: done (2 points), partially done (1 point) and not done (0 points). Checklist data will be summarised using descriptive statistics (i.e. proportions, means). Data relating to the 15-item checklist of needs will be summarised using descriptive statistics (i.e. proportions, frequencies, means), and outliers may be excluded as a sensitivity summary. Action plans (i.e. referrals/advice/further appointments) made during the structured review will be summarised using descriptive statistics (i.e. proportions, frequencies, means).
- Fidelity of receipt Self-reported experience of structured reviews will be scored against a
  pre-specified checklist (n= 9 items). Three response options are used: done (2 points),
  partially done (1 point) and not done (0 points). Self-reported experience of MLAS will be

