  scored using a set of questionnaires (6 questionnaires in total; 74 items). Four response
  options are used: agree, disagree, don't know, does not apply. Checklist data will be
  summarised using descriptive statistics (i.e. proportions, means).

Inter-rater reliability of fidelity of training and delivery data, specifically observations and audio-recordings will be assessed using percent agreement and Cohen's Kappa (95% CI):

$$\kappa_w = \frac{\sum v_{ij} \, p_{oij}}{\sum v_{ij} p_{eij}}$$

Where,

 $\kappa_w$ = agreement value (-1 to +1 ,where +1 represents perfect agreement between raters)  $v_{ij}$ = disagreement weight (quadratic weights)  $p_{oij}$ = is the proportion of the joint judgements

 $p_{eij}$  = is the proportion of judgements expected by chance

Intervention fidelity scores between 80-100% are classed as 'high', 51-79% 'moderate' and <50% as 'low'.

**Table 4**: Intervention fidelity components collected from participants and practices.

Intervention components	НСР	Participant
Structured review	$\checkmark$	$\checkmark$
	Duration/frequency: One-	
	off, up to 30min	
	Mode: Face-to-face	
15-item checklist of needs	$\checkmark$	$\checkmark$
		Sent before structured
		review
My Life After Stroke (MLAS)		$\checkmark$
		Duration/frequency: 6-week
		self-management course (2x
		individual appointments up
		to 45min each; 4x weekly
		group sessions up to 2.5hrs
		each)

		Mode: Face-to-face
Direct point of contact	$\checkmark$	$\checkmark$
service		Duration/frequency: As and
		when required
		Mode: Telephone
Service mapping tool	$\checkmark$	$\checkmark$
	Duration/frequency: As and	
	when required	
Optimised communication	$\checkmark$	
	Duration/frequency: As and	
	when required	
Healthcare professional	$\checkmark$	
training	Duration: Up to 2hrs	
_	Mode: Face-to-face	

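### SAP 10.2.1 (1), exploratory: as written, one model holds both stroke-review attendance and a 3-level action factor that already contains attendance, so their separate coefficients are not identified

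*SAP*

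**What the plan says.** SAP 10.2.1 restricts this work to one arm: "The intervention cohort will be considered as a separate sub-group analysis". Part (1) states its expectation in advance: "stroke review attendance and the level of action taken at a stroke review is associated with SIS handicap and emotion 12 month score". To examine it, the SAP names one linear mixed effect model, in the singular, built like the primary one. The terms listed are "fixed effects for the stroke review attendance (y/n), and categorical variable for action taken (no review, review with no action plan" and, as the last level, review with an action plan. No reference level, constraint or separate fit is mentioned.

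Part (2), on the self-management programme (MLAS), is built differently. Its model has "fixed effects for gender, baseline score and categorical variable MLAS compliance (yes, partial, no"), which is one 3-level exposure with no attendance term beside it.

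SAP 10.2 states the status of this work: "these secondary analyses are exploratory".

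**The concern.** The two terms carry overlapping information. A patient who did not attend is, by definition, in the no-review level, and a patient who attended is in one of the other two levels. Once the action factor is in the model, attendance adds nothing.

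The hypothesis names attendance and level of action as two exposures, so a reader will expect a coefficient for each. The model as written cannot supply both. Software will stop, or drop or constrain a column. If it drops an action column, that choice decides what the row labelled attendance means. SAP section 16 anticipates R Studio or Stata without choosing between them, and nothing in 10.2.1 settles the matter.

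What is at stake is the meaning of one coefficient in an exploratory table.

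**Working it through.** The SAP gives no figure here, so there is nothing to reproduce. The check is algebraic.

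**Inputs.** The two fixed effects and their levels are from SAP 10.2.1 (1), and the practice random effect is from SAP 10.1. For the numerical rank check: 23 practices × 20 patients = 460 intervention patients and an intraclass correlation of 0.03 (SAP section 7), with an assumed 30/20/50% split over the three levels. The group means below are assumed for illustration only.

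**Dependency.** Let D1 = review without plan, D2 = review with plan, A = attended. Then A = D1 + D2 for every patient.

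**Parameters against means.** With mean = β0 + αA + γ1D1 + γ2D2:

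- no review: μ0 = β0
- review, no plan: μ1 = β0 + α + γ1
- review, plan: μ2 = β0 + α + γ2

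There are three means and four parameters. Adding any constant to α and subtracting it from γ1 and γ2 leaves all three means unchanged. So α, γ1 and γ2 are not estimable one by one. Three combinations are estimable: α + γ1 = μ1 − μ0, α + γ2 = μ2 − μ0, and γ2 − γ1 = μ2 − μ1.

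**Rank, all three levels present.**

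| Fixed-effect columns | Columns | Rank |
|---|---|---|
| Intercept, A, D1, D2 | 4 | 3 |
| The same plus baseline score and gender | 6 | 5 |
| Information matrix of the first row with a practice random effect | 4 | 3 |
| Intercept, baseline score, gender, D1, D2 (no A) | 5 | 5 |
| Intercept, baseline score, gender, A, D2 (plan indicator) | 5 | 5 |
| Intercept, baseline score, gender, A alone | 4 | 4 |

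Neither covariates nor the random effect remove the dependency. The last three rows are the repaired forms, and each is full rank.

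**What attendance would mean.** Take indicator coding with no review as reference, and assumed means μ0 = 60, μ1 = 63, μ2 = 68.

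- D1 dropped: α = 63 − 60 = 3 and γ2 = 68 − 63 = 5. Attendance is review without plan versus none.
- D2 dropped: α = 68 − 60 = 8 and γ1 = 63 − 68 = −5. Attendance is review with plan versus none.
- A dropped: no attendance coefficient appears, and the action coefficients are 3 and 8.

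All three fits reproduce 60, 63 and 68 exactly. The two attendance values differ by 8 − 3 = 5 = μ2 − μ1, the plan-versus-no-plan difference, whatever the group sizes.

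**Two-model reading.** Attendance alone estimates a mixture of the two review groups. Ignoring covariates and the practice effect, and assuming 92 reviewed without and 230 with a plan, it gives (92 × 63 + 230 × 68)/322 − 60 = 66.57 − 60 = 6.57. It would be 3.71 at 276:46 and 7.29 at 46:276. The separate action model gives 3 and 8. Both models are identified, but this attendance effect is neither the 3 nor the 8 above.

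**The case against.** The strongest answer is that two models were meant. The paragraph names two exposures, and the action factor has its own no-review level, which it needs only if it stands alone. The SAP also uses the singular loosely: 10.1 says "Each domain will be modelled separately and the following model fitted", where one model covers two domains, and the model in 10.2.1 (1) must likewise serve both emotion and handicap. This is a fair reading, and under it there is no redundancy. But the paragraph joins both terms in one model and does not say that they are fitted separately. The skeleton tables listed in SAP section 19 have a part for this subgroup analysis and might settle it, but their content is not in the documents available.

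It can also be said that little turns on this. The hypothesis is one of association, which the joint test and group contrasts answer, and a rank deficiency would be noticed at fitting. That stands, and it limits the point to a minor one.

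Three stronger readings are tempting, and the documents do not support them. A reader might infer that the analysis is unusable or that the co-primary results are in doubt. Neither follows: every group contrast is estimable, and SAP 10.1 does not use these variables. A reader might also infer that the attendance coefficient could take almost any value or change sign. That needs codings which the SAP never names; the only coding it mentions is a dummy variable, for treatment group in 10.1. Finally, a reader might take rank 3 as certain for any data. It requires all three levels to occur. Protocol 7.1.1 expects each review to end in an action plan, so the no-plan level could be sparse. If it is empty the rank is 2, and attendance and plan are then the same variable.

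**Conclusion.** The point holds for the model as literally written. Attendance and the action factor are exactly collinear, the columns have rank 3 of 4 when all three levels occur, and the separate attendance and action coefficients are not identified. More patients would not cure it.

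Under indicator coding with no review as reference, the ambiguity in a reported attendance coefficient equals the plan-versus-no-plan difference: 5 points in the illustration, whose means are assumed. Fitted values, the joint 2-df test, the group contrasts and both co-primary analyses are unaffected.

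The severity is minor, and the conclusion rests on the one-model reading. If two models were intended, the remaining fault is that the SAP does not say so.

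**What to change.** First state whether one model or two is meant.

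- **One model, preferred form.** Delete the attendance term and keep the 3-level action factor, as 10.2.1 (2) does for MLAS. Report two contrasts from that fit: any review versus none, with its weights stated (equal weights, or the observed shares of reviewed patients with and without a plan), and plan versus no plan among those reviewed.
- **One model, equivalent form.** Use attendance plus a binary action-plan indicator, and note that the attendance coefficient then means review without plan versus none.
- **Two models.** Say so, and fit attendance and the action factor separately.

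In each case name the reference level. It would also help to say what is done if the no-plan level is empty or very small. The cost is a sentence or two of SAP text and, at most, matching table labels. No new data are needed, and in the one-model forms the contrasts come from the same fit.

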7.1.1. Structured Review of Patient Needs

A structured review will be performed by a Practice nurse or other appropriately trained member of the Practice team as part of the regular annual review recommended by current guidelines¹⁰. As part of the review, a 15-item checklist of post-stroke needs (see appendix A) will be sent by the Practice to the stroke survivor in advance. The survivor will be asked to tick all needs which apply to them, and to bring this with them to the appointment. At the review, the patient will be asked which of the ticked items is the most important and they would like to discuss most. Dependent upon time availability at the review, Practice staff will discuss and address up to three key needs identified by the survivor. A blank checklist will also be available in the Practice if needed.

The review will last approximately 20-30 minutes, and include a routine physical check-up based on QoF recommendations (e.g. blood pressure, record of immunisation, and medication review) followed by the discussion of up to three post-stroke needs as identified by the stroke survivor. The expected outcome of the review is an action plan agreed with the stroke survivor on how to address each of the needs identified in the review. A record of the checklist and the agreed action plan (e.g. referrals, agreed actions to be undertaken by the patient) will be kept in the patient records.

The patient will be provided with an information leaflet about the MLAS programme, with instructions on how to get further information from the MLAS team and how to access the programme.

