# 7 Sample Size

With 23 clusters per arm and an average of 20 patients per cluster, assuming an intra-class correlation of 0.03, a typical coefficient of variation of the cluster size of 0.65 (Campbell, 2014), and 2.5% significance (adjusted to 2.5% because of the use of two co-primary outcomes), we would be able to detect an effect size of 0.33 with at least 90% power on the co-primary outcomes (emotion and handicap sub-scales of the Stroke Impact Scale (SIS v3.0)). The sample size calculation has been inflated to allow for a rate of 20% loss to follow-up for patients within clusters. Loss to follow-up of entire clusters is not anticipated.

The conservative estimate of 20 patients per practice is drawn from the trials pilot data (unpublished) and the research groups experiences of running previous trials in this population (Fletcher K, 2010; Fletcher K, 2010; O'Brien C, 2013). A typical practice with a list size of between 7,000 to 10,000 will have approximately 100 - 150 patients on the stroke register (Progress in improving stroke care, 2010). We anticipate that the electronic search applying the exclusion criteria will eliminate around 40% of these (based on the pilot study) leaving 60 – 90 eligible patients per practice, of which about 30% will agree to take part (18 – 27 per practice). This will yield between 16 – 24 participants per practice.

The IPCAS trial was powered based upon the two co-primary outcomes (SIS emotional and handicap domains). It is important to be aware that the trial was not powered based on any secondary or exploratory end-points, and this should be considered in particular when interpreting any resulting p-values.

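### In the exploratory structured-review model, the plan versus no-plan contrast may carry residual confounding by need, because no measure of need is a listed covariate

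*SAP*

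**What the plan says.** SAP 10.2.1 treats the intervention arm as a subgroup and states an a priori hypothesis that the dose of intervention is associated with SIS outcome. Item 1 (Structured Stroke Review) applies this to review attendance and the level of action taken. The model is to follow the primary analysis, with fixed effects for attendance (yes/no) and a "categorical variable for action taken (no review, review with no action plan, review with action plan".

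Protocol 7.1.1 says how a plan arises: "The expected outcome of the review is an action plan agreed with the stroke survivor on how to address each of the needs identified". The patient is sent a 15-item checklist beforehand, ticks the needs that apply and brings it along. Up to three needs are discussed, as time allows. The checklist and the plan are kept in the patient record.

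The only stated use of checklist content is descriptive (SAP 10.2.1, item 3, fidelity of delivery): "Data relating to the 15-item checklist of needs will be summarised using descriptive statistics". Need is not among the covariates in SAP 8.3, SAP 10.1 or the review model itself. SAP 10.1 does include the baseline score of the same SIS domain. SAP 10.2 calls the secondary analyses exploratory.

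**The concern.** A plan is a response to need. A reviewed patient who raises no need has little or nothing to plan for, while one who raises several is likely to leave with a plan. If need at the review also predicts 12-month emotion or handicap beyond what the model adjusts for, the plan coefficient absorbs part of that difference. This is confounding by indication, and its likely direction is against the intervention: a useful plan may look useless or even harmful.

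Baseline SIS score is an incomplete guard. Each model would carry the score for one domain, whereas the checklist in Protocol Appendix A also covers pain, stiffness, mobility, continence, cognition and fatigue. Baseline SIS is collected before practice randomisation (Protocol 9.1) and the review comes later, so needs arising in between are missed. It is also unclear that baseline score enters this model. The neighbouring MLAS model, likewise fitted in line with the primary analysis, names baseline score and gender explicitly; the review model names neither.

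At stake is how one exploratory, non-randomised contrast is interpreted.

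**Working it through.** **1. The plan's own design figure.** SAP 7 gives these inputs:

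- Number of practices, their size and the ICC: "With 23 clusters per arm and an average of 20 patients per cluster, assuming an intra-class correlation of 0.03".
- Variation in practice size (CV below): "a typical coefficient of variation of the cluster size of 0.65".
- Test level: "2.5% significance (adjusted to 2.5% because of the use of two co-primary outcomes". Sidedness is not stated; two-sided is taken here.
- Claimed performance: "we would be able to detect an effect size of 0.33 with at least 90% power".
- Attrition: the calculation is "inflated to allow for a rate of 20% loss to follow-up for patients within clusters".

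The check:

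- Design effect = 1 + ((CV² + 1)m - 1) × ICC.
- m = 20: 1 + (1.4225 × 20 - 1) × 0.03 = 1.82. Effective n per arm = 460/1.8235 = 252.3; power 92.9%.
- m = 16 (after 20% loss): 1 + (1.4225 × 16 - 1) × 0.03 = 1.65. Effective n per arm = 368/1.6528 = 222.7; power 89.3%.

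The stated figure reproduces to within a percentage point. It concerns the randomised comparison, and nothing below alters it.

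**2. Size of the possible confounding.** The documents give no inputs, so all of the following are assumptions. Let U be need at the review (SD 1) and B the baseline SIS score (SD 1), with B correlated -λ with U.

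- 12-month score: Y = 0.5B - γU + 0.8e, then scaled to SD 1.
- Log-odds of having a plan: 1 + sU.
- True plan effect: zero.
- 400,000 simulated reviewed patients per setting, linear model, no clustering.

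Apparent plan effect in SD, adjusted for baseline score, with s = 1 (about 70% have a plan):

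| λ | γ = 0 | γ = 0.1 | γ = 0.2 | γ = 0.3 |
|---|---|---|---|---|
| 0.3 | -0.002 | -0.077 | -0.154 | -0.227 |
| 0.5 | 0.003 | -0.068 | -0.128 | -0.188 |
| 0.7 | 0.001 | -0.046 | -0.090 | -0.131 |
| 0.9 | 0.000 | -0.015 | -0.035 | -0.049 |

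- With no covariates, the same settings give -0.137 to -0.566.
- With baseline score and need both in the model, every setting is within 0.005 of zero.
- At λ = 0.5 and γ = 0.2, moving s through 0, 0.5, 1 and 2 gives 0.000, -0.072, -0.128 and -0.203 with baseline adjusted.

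The bias is zero if need adds nothing to prognosis beyond baseline score (γ = 0), or if need does not influence having a plan (s = 0). The complete removal in the last model is a best case, because need is measured there without error; a checklist count would remove less.

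**3. Can both review terms be fitted?** Attendance (yes/no) equals the sum of the indicators for review without plan and review with plan. With an intercept, that makes four columns of rank 3. The two terms cannot be estimated together.

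**The case against.** The strongest counter-argument is that the SAP claims little here. It speaks of association, labels the secondary analyses exploratory, acknowledges that patients partly choose their exposure, and enters action taken as an unordered category with no trend test. Following the primary analysis most naturally brings in the baseline score of the same domain, and checklist items on mood, family relationships and social activities overlap with emotion and handicap. Other needs confound only if they predict the outcome beyond that score, which the documents do not show. All of this stands, and it limits the point to residual confounding.

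A reader might infer that the no-plan group is essentially the low-need group. The documents do not support that. Needs are addressed as time allows (Protocol 7.1.1), and Protocol 11.1 tracks development of action plans as fidelity data and anticipates operational and staffing problems. A missing plan may therefore mean a plan not delivered. The SAP does not separate the two cases.

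A reader might also infer a spurious effect as large as the trial's planned 0.33 SD with the sign reversed. Taking a residual correlation r of 0.10 to 0.20 between plan and outcome, a residual SD of 0.76 and a proportion p of 20 to 30% without a plan, r × 0.76/√(p(1-p)) runs from 0.10 × 0.76/√0.21 = 0.17 to 0.20 × 0.76/√0.16 = 0.38. But that assumes the confounding it sets out to show and excludes zero by construction; none of its inputs is in the documents.

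What remains is that the SAP's wording about dose and level of action invites a causal reading, and that a recorded variable bearing directly on who gets a plan is left out of the model.

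**Conclusion.** The plan versus no-plan contrast is open to residual confounding by need, probably in the direction of making plans look less helpful. On the assumed inputs above, the spurious difference is 0 to about -0.2 SD (largest value -0.23) with baseline SIS adjusted, and larger if it is not. Zero is a possible answer.

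It does not follow that the result will be misread as an effect of the plan, or that the stated hypothesis cannot be addressed: the hypothesis is one of association, which a correctly specified model can estimate. Only a causal or dose-response reading would be unsafe. The randomised co-primary comparison is unaffected. This is a cheap improvement to one exploratory model.

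**What to change.** In SAP 10.2.1(1):

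- State that baseline score and the other primary-model covariates enter this model.
- Fit review attendance and action plan as separate contrasts, since the two terms are collinear.
- Compare plan with no plan only among reviewed patients with at least one ticked need, adjusting for the number of checklist needs. Adjusting for the count among all reviewed patients would rely on extrapolation, because those with no need have little or nothing to plan for.
- Report reviewed patients with no need separately from those with need but no plan.
- Describe the results as non-causal associations and do not present the three categories as a dose scale.

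The cost is SAP wording; the checklist is already kept and due to be summarised. Patients with no recorded checklist leave this one exploratory model, which may introduce some selection, so their number should be reported. The count is an imperfect measure of need, so some confounding may remain.
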